---

## Foreword

This document is intended to describe a University of Queensland (UQ) trial and to provide information about procedures for screening, enrolling and treating trial participants. It is not intended that the protocol be used as a guide for the treatment of patients who are not enrolled on this trial.

UQ will not accept any data for analysis unless each Trial Site has HREC approval for patient enrolment and participation in this trial.

## Abbreviations

AE	Adverse Event
CRF	Case Report Forms
QOL	Quality of Life
DLQI	Dermatology Quality of Life Index
GCP	Good Clinical Practice
HIV	Human Immunodeficiency Virus
HREC	Human Research Ethics Committee
ICH	International Conference on Harmonisation
PI	Principal Investigator
PICF	Participant Information Sheet and Consent Form
PRO	Patient Reported Outcome
QA	Quality Assurance
QiDerm	Queensland Institute of Dermatology
SAE	Serious Adverse Event
SOP	Standard Operating Procedure
TEAE	Treatment Emergent Adverse Events
TGA	Therapeutic Goods Administration
TMC	Trial Management Committee
UAE	Unexpected Adverse Events
UQ	University of Queensland

## Trial Summary

[figure not shown]
Data category	Information	
Trial Registry	Registry Name	Australian New Zealand Clinical Trials Registry (ANZCTR)
	Trial Identifying No	TBC
	Date of registration	TBC
	Registry Name	ClinicalTrials.gov
	Trial Identifying No	TBC
	Date of registration	TBC
Secondary identifying numbers		
Source(s) of monetary or material support	The University of Queensland	
Primary sponsor contact details		
Contact for public queries	[name] [contact]	
Contact for scientific queries	[name] [contact]	
Public title	IxeHeal	
Scientific title	Phase II Study of Ixekizumab for Chronic Venous Ulcers	
Countries of recruitment	Australia	
Health condition(s) or problem(s) studied	Treatment of Chronic Venous Ulcers	
Intervention(s)	To perform a Phase II randomized double blind placebo controlled trial, using Ixekizumab, in patients with treatment-resistant chronic venous ulcers	

Key Eligibility criteria
	
Inclusion
 
 
1. Aged 18 years or older.
 
2. Patients who are willing to read or comprehend and sign a voluntary consent for research
 
3. Patients with Chronic Venous Ulcers that have failed to respond to Standard Therapy including Compression for 4 weeks
 
 
Exclusion
 
 
1. Arterial insufficiency: Ankle-Brachial pressure index <0.7
 
2. Diabetes
 
3. Pregnancy
 
4. Crohn's Disease
 
5. Ulcerative Colitis
 
6. Infection or excessive colonization of ulcer in past 2 months
 
7. Patients whose neutrophil count is not WNL
 
8. Patients who have active Tuberculosis (positive QFT-G)
 
9. Patients currently being treated for malignancy
 
10. Patients with chronic or recurrent candidiasis infection
 
11. Patients who have inflammatory bowel disease (IBD)
 
12. Women of childbearing age
 
13. Any contraindication to therapy
 
14. Life expectancy of less than 6 months due to chronic illness
 
 
Any other condition as defined by the investigator which significantly impact the patient's suitability in this study such as the use of cytotoxic medication, inability to present to study visits due to distance.

--	--

Study type	Phase II randomized double blind placebo controlled trial
Target sample size	28 patients
Primary outcome(s)	A 40% reduction in ulcer size after 12 weeks compared to the initial wound size.
Key secondary outcomes	
Drug related adverse events and serious adverse events at 12 weeks.
 
Percentage reduction in ulcer size at 12 weeks compared to the initial wound size.
 
Percentage patients with healed ulcers
 
Time to ulcer healing
 
Percentage and absolute reduction in Pain score (0-10)
 
Dermatology life Quality Index DLQI
 
Compliance with compression
 
Treatment-related reduction of IL17 levels in wound fluid and biopsies*
 
Wound-infiltrating macrophage phenotype change from M1 to M2*
 
Alterations in wound microbiome

Trial analyses timelines	
Interim Analysis: After the first 14 patients have completed the 12 weeks of Intervention
 
Final Analysis: After the full 28 patients have completed the 12 weeks of Intervention

## Trial schema

# 1 INTRODUCTION AND BACKGROUND

Inflammation is one of the early phases of wound healing and is an evolutionarily conserved process. It is mainly driven by macrophages and neutrophils, as well as a small sub-population of T cells. Many studies have demonstrated that inflammation is an essential phase of the healing process and depletion of macrophages classically results in delayed healing. At the same time, however, many chronic wounds display excessive inflammation which has been shown to impede healing. Excessive inflammation is established as an etiologic factor in venous leg ulcers as a result of iron oxide deposition in the dermis due to venous hyper pressure and red blood cell extravasation. This excessive inflammation results in matrix and growth factor degradation through the action of proteases and reactive oxygen species. Additionally, in diabetic wounds, excessive inflammation down modulates insulin/IGF1 signalling, preventing the proper response of epidermal cells to growth factors.

Wound closure requires the transition of macrophages from an inflammatory state (M1) to a pro-healing state (M2) during the course of healing. Using gene expression array studies on sorted M1 and M2 macrophage populations from skin wounds we have demonstrated that IL17-IL23p19 signalling maintains wound macrophages in an inflammatory stage and promotes excessive recruitment of neutrophils.

## 1.1 Previous Studies

Our preclinical experiments have demonstrated the following points of validation:

1. IL17-/- mice heal faster than wild-type (Rodero et al. 2013).
2. IL17-/- mice on an obese diabetic background heal faster than wild-type (Lee et al. 2017)
3. Diabetic mice treated with anti-IL17 blocking antibodies heal faster than wild-type (Rodero et al. 2013).
4. p19-/- mice do not display any IL17 in their wounds (Lee et al. 2017)
5. Diabetic mice treated with anti-p19 antibodies have reduced IL17 in their wounds and heal faster than wild-type (Lee et al. 2017).
6. IL12 (p35) and IL12/23(p40) deficient mice have delayed healing (unpublished).

Results of a recent, small clinical pilot study by others showed that TNF blocking antibodies promoted closure of chronic wounds (Fox et al., 2016), providing preliminary support for the hypothesis that excessive inflammation prevents chronic wound healing.

Taken together, these preclinical data and preliminary clinical findings provide strong support for our idea of using p19 or IL17 blocking antibodies to promote chronic wound healing.

# 2 TRIAL OBJECTIVES

## 2.1 Research Hypothesis

**HYPOTHESIS:** The IL23(p19)-IL17 axis is strongly involved in the maintenance of macrophages in an inflammatory state (M1) in chronic wounds, preventing wound progression to a repair stage. By stimulating the transition of macrophages from the pro-inflammatory (M1) to pro-healing (M2) phenotype, blockade of IL17 or IL23 (p19) will, therefore, accelerate closure of treatment-resistant chronic wounds.

## 2.2 Objectives

To evaluate the safety and efficacy of Ixekizumab over placebo at 12 weeks in a randomized double blind trial on patients with chronic venous ulcers failing well conducted standard of care therapy.

The evaluation encompasses wound size reduction, pain reduction, quality of life improvement as well as biological measures of inflammation reduction.

Regarding safety, specific emphasis will be on infections and changes in microbiome.

## 2.3 Endpoints

### 2.3.1 Primary Endpoints

The primary endpoints are

- A 40% reduction in ulcer size at 12 weeks as compared to initial size. Size changes are measured using digital 3D photography and wound size evaluation device. It is expected that significantly more patients will achieve the primary end-point at 12 weeks in the Ixekizumab group compared to the placebo group.

### 2.3.2 Secondary Endpoints

- Drug related adverse events and serious adverse events at 12 weeks.
- Percentage reduction in ulcer size at 12 weeks compared to the initial wound size.
- Percentage patients with healed ulcers
- Time to ulcer healing
- Percentage and absolute reduction in Pain score (0-10)
- Changes in Quality of life DLQI score
- Compliance with compression
- Treatment-related reduction of IL17 levels in wound fluid and biopsies\*
- Wound-infiltrating macrophage phenotype change from M1 to M2\*
- Alterations in wound microbiome

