## 12 ADVERSE EVENT REPORTING

### 12.1 Definitions

**Adverse Event (AE):** An AE is any untoward medical occurrence (toxicity, sign or symptoms) in a patient administered a study treatment; the event does not necessarily have a causal relationship with the treatment.

**Serious Adverse Event (SAE):** An SAE is any untoward medical occurrence that occurs after administration of the Ixekizumab .

- Results in death
- Is life-threatening (an event in which the participant was immediately at risk of death *at the time of event*)
- Requires in-patient hospitalisation or prolongation of existing hospitalisation
- Results in persistent or significant disability/incapacity
- Is a congenital anomaly/birth defect
- Important medical event (events may be considered a serious adverse experience if they require medical or surgical intervention to prevent one of the listed definitions, e.g. an 'allergic bronchospasm' which required intensive treatment in an emergency room or at home)

An event will not be considered to be a SAE if;

- Hospitalisation is due to pre-trial scheduled elective surgery
- Out-patient hospitalisation for procedures such as:
  - Elective day surgery
  - Convenience purposes (e.g. transportation difficulties)

**Serious Adverse Reaction (SAR):** A serious adverse reaction is an SAE that is suspected as having a causal relationship to the trial treatment, as assessed by the investigator responsible for the care of the patient. A suspected causal relationship is defined as possibly, probably or definitely related (see definitions of causality table).

**Related Unexpected Serious Adverse Event:** An adverse event that meets the definition of serious and is assessed by the Principal Investigator or nominative representative delegated and trained by the Principle Investigator as:

Related	that is, it resulted from administration of any of the research procedures
Unexpected	that is, the type of event is not listed in the protocol as an expected occurrence

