### Definitions of causality:

Relationship	Description
Unrelated	There is no evidence of any causal relationship with the trial treatment
Unlikely	There is little evidence to suggest there is a causal relationship (e.g. the event did not occur within a reasonable time after administration of the trial treatment). There is another reasonable explanation for the event (e.g. the patient's clinical condition, other concomitant treatment)
Possible	There is some evidence to suggest a causal relationship (e.g. because the event occurs within a reasonable time after administration of the trial treatment). However, the influence of other factors may have contributed to the event (e.g. the patient's clinical condition, other concomitant treatments)
Probable	There is evidence to suggest a causal relationship, and the influence of other factors is unlikely
Definitely	There is clear evidence to suggest a causal relationship, and other possible contributing factors can be ruled out

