## 12.2 REPORTING

### 12.2.1 Adverse Events (AE)

Adverse events are to be reported following any injection of Ixekizumab, which must be graded according to The National Cancer Institute (NCI) Common Terminology Criteria for Adverse Events (CTCAE) version 5.0 (Appendix) by a study investigator. For each AE, the highest grade observed since the last visit should be reported on the relevant CRF.

All adverse events shall be recorded in the trial database via adverse event CRFs. Internal statistical analysis of these data shall be performed at the times specified in the protocol and investigators and responsible HRECs will be advised of any safety issues which emerge during this process.

Of note, all serious adverse events are to be reported within 24 hours to Lilly Ltd who provides the drug for this study.

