### **12.2.2 Serious Adverse Events (SAE)**

SAEs are to be reported by the trial site immediately and no more than 24 hours of being notified, from the commencement of injection until the last visit. Date of the SAE occurrence and date notified must be documented.

The investigator at the trial site is responsible for;

- grading the event according to the NCI CTCAE v 5.0
- identifying the seriousness of the adverse event
- identifying the causal relationship to the treatment and
- determining the expectedness according to the treatment

The investigator is also responsible for notifying responsible HRECs, Research Governance Officers or other appropriate regulatory authorities of the SAE according to local ethical and regulatory guidelines. They are also to follow up the event (with regular reporting) until resolved. Please see figure 1.

[figure not shown]
The Sponsor shall;

- Arrange for the trial chairperson and/ or a clinical reviewer to review the event and confirm causal relationship and expectedness
- Report applicable events to the regulatory authorities (e.g Therapeutic Goods Administration of Australia (TGA))

Notify all other participating investigators of any serious unanticipated related adverse events and any action taken

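### The only adverse-event endpoint is limited to drug-related events, so non-serious infections, which the objectives emphasise, enter or leave the comparison by causality judgement

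*Protocol*

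**What the plan says.** Section 2.3.2 lists one adverse-event endpoint: "Drug related adverse events and serious adverse events at 12 weeks". The Trial Summary words it the same way, so it is not a slip in one place. Section 2.2 makes safety against placebo part of the objective and adds: "Regarding safety, specific emphasis will be on infections and changes in microbiome". The microbiome then has its own secondary endpoint; infections have none. Section 9.2, which sets out the comparisons between arms, contains no safety comparison.

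Section 12.1 defines an adverse event irrespective of cause ("the event does not necessarily have a causal relationship with the treatment"). For serious adverse reactions it sets a threshold: "A suspected causal relationship is defined as possibly, probably or definitely related". No threshold is given for the endpoint. Section 12.2.2 makes the site investigator responsible for "identifying the causal relationship to the treatment and" other tasks, but says so for serious events only. The causality table allows a rating of Unlikely where "There is another reasonable explanation for the event", and gives the patient's clinical condition as an example.

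On data collection, Section 12.2.1 states: "All adverse events shall be recorded in the trial database via adverse event CRFs". It also provides for an internal statistical analysis of these data, and Section 13.4 has the independent safety committee review them.

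**The concern.** In a placebo-controlled trial the placebo arm supplies the background rate of infection, so comparing the arms does not require anyone to decide which infections the drug caused. Filtering by attribution takes events out of a randomised comparison on the strength of individual judgements.

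The filter matters here because every participant has a chronic open ulcer. That is a ready alternative explanation for an ulcer infection or cellulitis, and these belong to the class of event that the objectives emphasise. At stake is how well the trial's own safety endpoint can show an excess of infections on ixekizumab. It is a secondary endpoint, but it is the only one that carries adverse events.

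**Working it through.** **Step 1: what the endpoint covers.** Its wording can be read in two ways.

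- Drug-related adverse events and drug-related serious adverse events. All infections are then filtered.
- Drug-related adverse events, plus all serious adverse events. Serious infections are then counted whatever the cause, and non-serious ones are filtered.

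Non-serious infections are filtered on both readings.

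**Step 2: how the filter treats an infection.** The two relevant rows of the causality table, side by side:

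| Row | Evidence of causality | Role of the patient's clinical condition | Related under the threshold for serious adverse reactions? |
|---|---|---|---|
| Unlikely | little, for example poor timing | another reasonable explanation | no |
| Possible | some, for example reasonable timing | a factor that may have contributed | yes |

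The patient's clinical condition appears on both sides of the line between related and not related. An ulcer infection can be placed in either row without breaking a rule.

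**Step 3: size of the effect.** The plan gives no figure to reproduce, so this is an illustration.

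- From the documents: 28 patients in two equal groups (Section 9.1), so n = 14 per arm.
- Assumed, not in the documents: infection risk pC on placebo and pT on ixekizumab, and the share q of patients with an infection whose infection is judged drug related. Because attribution is blinded, q is taken as equal in the two arms.
- Expected patients counted per arm = 14 × p × q.
- Risk difference seen by the endpoint = q × (pT − pC).

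For 10% and 30% with q = 1: 14 × 0.10 = 1.4 and 14 × 0.30 = 4.2, a difference of 20 points. With q = 0.5: 0.7 and 2.1, or 10 points. With q = 0.25: 0.35 and 1.05, or 5 points.

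The last column is the power of a two-sided Fisher exact test at 0.05, computed exactly with risks q × pC and q × pT:

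| pC, pT | q | Expected counts | Difference (points) | Power |
|---|---|---|---|---|
| 10%, 30% | 1 | 1.4 v 4.2 | 20 | 0.14 |
| | 0.5 | 0.7 v 2.1 | 10 | 0.02 |
| | 0.25 | 0.35 v 1.05 | 5 | 0.002 |
| 10%, 50% | 1 | 1.4 v 7.0 | 40 | 0.54 |
| | 0.5 | 0.7 v 3.5 | 20 | 0.14 |
| | 0.25 | 0.35 v 1.75 | 10 | 0.02 |
| 20%, 60% | 1 | 2.8 v 8.4 | 40 | 0.44 |
| | 0.5 | 1.4 v 4.2 | 20 | 0.14 |
| | 0.25 | 0.7 v 2.1 | 10 | 0.02 |

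The ratio of risks does not change (4.2/1.4 = 2.1/0.7 = 3). What shrinks is the absolute difference and the number of events behind it.

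**The case against.** The strongest reply is that the data are not lost. All adverse events are recorded, Section 12.2.1 promises an analysis of them, cellulitis and adverse events are scheduled at every treatment visit in Section 7.1, and the safety committee sees the reports. All of this stands. A table of all events by arm may also be in a statistical analysis plan that is not shown, and nothing in the protocol forbids one. But the point does not rest on a missing table. The protocol states its safety endpoint, and states it more narrowly than its own definition of an adverse event and its own objective.

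A reader might infer that the causality table removes almost every ulcer infection. It does not. Injections are two weeks apart up to week 12, so most infections on treatment fall soon after a dose, which points to Possible. If the threshold for serious adverse reactions is carried over to the endpoint, Possible counts as related. The table permits exclusion but does not require it.

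A reader might also infer that the filter favours ixekizumab. The trial is double blind, and nothing in the protocol suggests that attribution would differ by arm. Dilution is the supportable harm.

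Finally, even with every infection counted, power is 0.14 for 10% against 30%. A trial of this size cannot test infection risk formally under either endpoint. That stands too, and it limits how much the change can gain.

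**Conclusion.** The point holds as a badly chosen endpoint. Non-serious infections reach the only adverse-event endpoint through a causality judgement that the protocol's own table leaves open, and whether serious infections are filtered as well cannot be settled from the wording. With equal attribution in the two arms, the absolute difference shrinks to the fraction q of its true size, whatever the rates. The 20-to-10-point example rests on assumed rates and an assumed share of one half.

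The documents do not support saying that infections are necessarily dropped, that serious events are certainly restricted, or that a true excess would go unseen. Section 2.2 speaks of infections in general, not of ulcer infections alone, and does not rank them as the main safety concern. The matter should be corrected, but it touches neither the primary endpoint nor the collection of data.

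**What to change.** In Section 2.3.2 and the Trial Summary, define the endpoint as all adverse events, all serious adverse events and all infections (including ulcer infection and cellulitis) after the first injection of study product, by randomised arm and regardless of causality. Keep drug-related events as a supporting table, and state which causality grades count as related.

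Align Sections 12.1 and 12.2.1 at the same time. They tie the definition of a serious adverse event and the reporting of adverse events to ixekizumab alone. Both should refer to study product (ixekizumab or placebo), so that the two arms are covered by the same words.

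The cost is wording changes in these sections and one extra table. No visit or assessment is added, because adverse events are already scheduled for both arms in Section 7.1. The comparison should be presented as descriptive.

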## 3 TRIAL DESIGN

Patients with a diagnosis of venous ulcer at the participating wound clinics will be considered and treated with standard compression therapy and dressing for 4 weeks. Those not responding to treatment with wound surface reduction <20% will be included and randomly assigned, using double blind technique, to treatment and placebo groups. All participants will receive standard of care treatment for chronic, non-healing wounds, comprising compression dressings changed as required. In addition to standard of care treatment, participants will receive either Ixekizumab or placebo via subcutaneous injection.

### 3.1 Dosing Regimen

Cohorts of patients with chronic venous ulcers (n = 28) will be randomly assigned to treatment and placebo groups, both receiving compression treatment and standard dressing and therapy of wounds.

Ixekizumab or placebo will be injected subcutaneously (prefilled syringe format) in two 80 mg injection at week 0, followed by single 80mg injections at weeks 2, 4, 6, 8, 10 and 12. This corresponds to standard dosing regimen performed in psoriasis.

### **3.2 Choice of Comparator**

Patients receiving placebo will be the comparators in this study.

## **4 PARTICIPANT SELECTION AND ELIGIBILITY**

### **4.1 Source of participants**

Participants will be recruited for the study the Queensland Institute of Dermatology Brisbane and other reliable Wound Care Clinics in Brisbane.

### **4.2 Accrual Numbers and Timelines**

It is anticipated it will take 9 months to complete target accrual of 28 participants. Duration for individual patients on study will be approximately 16 weeks this includes the inclusion criteria of 4 weeks of unsuccessful compression bandaging.

### **4.3 Eligibility Criteria**

Patients (or a representative) must provide written, informed consent before any screening or study procedures occur.

Patients will be eligible if they meet all of the inclusion criteria and none of the exclusion criteria. Inclusion and exclusion criteria will be checked at prior to and at randomisation, and only those patients that still meet the criteria will be included. No exceptions, waivers or exemptions will be granted.

#### **4.3.1 Inclusion Criteria**

1. Aged 18 years or older.
2. Patients who are willing to read or comprehend and signed a voluntary consent for research.
3. Patients with at least one venous leg ulcer defined as any break in the skin that had either been present for longer than 6 weeks or occurred in a person with a history of venous leg ulceration. Ulcers are judged purely venous if no other cause is suspected. The ulcer is required to be venous in appearance (moist, shallow, and of an irregular shape) and to lie wholly or partly within the gaiter region of the leg where varicosities or purpuric and pigmented skin can be identified.
4. Patients with Chronic Venous Ulcers that have failed to respond (<20% closure) to Standard Therapy including Compression 4 weeks

